5.4.2.3.3 Growth

Growth assessments will include height and weight measurements of each participant outlined in the SoA. The height of both biological parents will be obtained to determine the participant's growth potential. The participant may continue in the study without these data and/or consent to obtain, use, and disclose parental personal data.

5.4.2.4 Pharmacokinetic Endpoints

The primary PK endpoints for GZR and EBR are steady-state plasma AUC_{0-24} , C_{max} , C_{trough} , and CL/F . Additional steady-state PK parameters such as plasma concentration immediately predose (C_{trough}) and T_{max} will also be estimated.

5.4.2.5 Future Biomedical Research

The Sponsor will conduct Future Biomedical Research on specimens consented for future biomedical research during this clinical trial. This research may include genetic analyses (DNA), gene expression profiling (RNA), proteomics, metabolomics (serum, plasma) and/or the measurement of other analytes, depending on which specimens are consented for future biomedical research.

Such research is for biomarker testing to address emergent questions not described elsewhere in the protocol (as part of the main trial) and will only be conducted on specimens from appropriately consented participants. The objective of collecting/retaining specimens for Future Biomedical Research is to explore and identify biomarkers that inform the scientific understanding of diseases and/or their therapeutic treatments. The overarching goal is to use such information to develop safer, more effective drugs/vaccines, and/or to ensure that participants receive the correct dose of the correct drug/vaccine at the correct time. The details of this Future Biomedical Research sub-trial are presented in Appendix 6 – Collection and Management of Specimens for Future Biomedical Research.

5.4.3 Rationale for the Use of Comparator/Placebo

This is an open-label trial of the safety and efficacy of the combination of EBR and GZR. The current pediatric standard of care is PR. Comparisons will be made to historic efficacy rates and safety profile in pediatric PR clinical trials [Kelly, D. A., et al 2011] [Wirth, S., et al 2010] [McHutchison, J. G., et al 2009].

As discussed in Section 3.2.2.1, the response rates for HCV in children are comparable to response rates in adults. With an all-oral DAA regimen, the medications directly interact with the virus and are not impacted significantly by host response. This is most clearly demonstrated by the minimal impact of race, gender, and IL28B status on efficacy of EBR/GZR in the adult program (see IB). Safety profile will be established without a comparator. PR has a well characterized safety profile in both adults and children.

5.5 Justification for Dose

5.5.1 Starting Dose for This Trial

Mini Age Cohort 1 (aged 12 to less than 18 years) will start with the adult FDC EBR/GZR (50 mg/100 mg) dose. Mini Age Cohort 2 (aged 7 to less than 12 years) is planned to start with the pediatric formulation of EBR/GZR (30 mg/60 mg). Based on the PK analyses from Mini Age Cohort 1 and 2, dosing recommendations will be provided by weight bands for Mini Age Cohort 3 and Expanded Age Cohort 1. Similarly, as described below, dosing regimens for Expanded Age Cohorts 2/3 will be developed based on the population PK model and dosing recommendations will be provided by weight bands. Weight bands for Mini Age Cohort 3 and the Expanded Age Cohorts will be determined by PK analyses. See Section 7.1 for a description of EBR/GZR adult FDC dose versus the pediatric formulation.

5.5.1.1 Dose Justifications

Since the relationship between exposure and safety and efficacy is well-established for EBR and GZR in adults, achieving AUC exposures in pediatric patients that is similar to adults is anticipated to result in similar safety and efficacy profile as adults. Therefore, the target dose in each pediatric age group is one that yields AUC exposures similar to that obtained in adults who receive EBR (50 mg) and GZR (100 mg).

Similarity between pediatric and adult AUC will be assessed based on the GM AUC values. The pediatric GM AUC should be approximately within 2-fold that estimated in adults for EBR and GZR. Additionally, the pediatric GM AUC range should fall within the defined clinical bounds for EBR [0.5, 2.0] and GZR [0.4, 5.0]. Therefore, the pediatric GM AUC for each age group should fall within ~0.81-8.6 $\mu\text{M}^*\text{hr}$ for GZR and ~1.1-4.4 $\mu\text{M}^*\text{hr}$ for EBR, which corresponds to the AUC associated with the lower and upper clinical bounds. Otherwise, the dose will be adjusted for the Expanded Age Cohorts so that the AUC falls within the clinical bounds.

For EBR and GZR, CYP3A, P-gp, and OATP1B1/3 are the known enzymes/transporters to consider when thinking about potential age-related PK changes in the pediatric population. Children >7 years of age have mature CYP3A enzymes that are comparable to those of adults [Ince, I., et al 2013], with minor incremental maturation of CYP3A in children 3-7 years of

age [Johnson, T. N., et al 2006]. OATP1B1 protein expression is not age dependent in the range of 9 days to 12 years [Thomson, M. M., et al 2016], or in the range of 7 to 70 years [Prasad, B., et al 2014], and OATP1B3 protein expression was also not age dependent in the range of 2 to 12 years [Thomson, M. M., et al 2016]. These observations indicate that minimal to no age-related changes related to enzyme/transporter expression or maturation for EBR and GZR are anticipated in the age range of 3-18 years compared to adults.

5.5.1.2 Dose in Mini Age Cohort 1 and 2

The adult Phase II/III clinical program included patients with body weight down to 37 kg, who demonstrated favorable PK, safety, and efficacy. Based on the comparable body weight and CYP3A and OATP1B maturation in participants aged 12 years up to 18 years, participants in Mini Cohort 1 will be administered the adult FDC dose of EBR/GZR (50 mg/100 mg), which is anticipated to result in comparable exposures to adults.

The EBR and GZR PBPK models developed for the adult program were used to estimate exposures in pediatric HCV patients from 12 to 18 years of age. The pediatric simulations assumed the same OATP1B/3 factor for hepatic uptake as estimated for adult patients. The simCYPTM program used for the PBPK model accounts effects of physiology (eg, body weight, liver size) age-related CYP3A abundance, and HCV infection in these pediatric participants on PK. The PBPK model suggests that the adult dose of EBR/GZR (50 mg/100 mg) would result in comparable plasma exposures in 12-18 year olds as in adults.

The EBR and GZR PBPK models were also used to estimate exposures in pediatric HCV patients from 7 to 12 years of age. A dose of 30 mg and 60 mg for EBR and GZR, respectively, in pediatric HCV patients from 7 to 12 years of age is estimated to result in comparable AUC exposures as adult HCV patients that are administered the FDC. The starting dose for Mini Age Cohort 2 may be refined, if needed, based on the estimated Day 1 AUC from Mini Age Cohort 1.

5.5.1.3 Dose in Mini Age Cohort 3 and Expanded Age Cohorts 1, 2, and 3

The doses in these cohorts will be determined based on cumulative pediatric PK data and population PK and PBPK modeling and simulation. The Day 1 and TW4 PK data from Mini Age Cohorts 1 and 2 will be used to estimate the AUC for these participants and will be incorporated in the population PK and PBPK models.

The models will then be used to estimate the anticipated exposure and select optimal doses for Mini Age Cohort 3 and Expanded Age Cohort 1. PK data from these cohorts will in turn be used to update the model, and select the dose for Expanded Age Cohort 2/3. Dosing recommendations for Mini Age Cohort 3 and the Expanded Age Cohorts will be provided by weight bands, which will be determined by PK analyses. At each step, the goal of model-based simulations will be to derive a dosing regimen expected to provide similar exposures in pediatric patients as in adults.

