3.2.4 Preclinical Trials Supporting a Pediatric Clinical Study

Prior to initiation of the pediatric clinical trial, pre- and postnatal developmental EBR and GZR monotherapy studies have been conducted and have not identified findings of concern in rats, rabbits, and dogs. In rats, dosing did not result in any effects on development, growth, behavior, reproductive performance, or fertility following oral administration to female rats from Gestation Day 6 through Lactation Day 20. In these studies, the highest maternal GZR exposure, area under the time-concentration curve over 24 hours (AUC_{0-24}) = 155 $\mu\text{M}\cdot\text{hr}$ represents approximately 31-fold the GZR clinical target AUC_{0-24} of 5 $\mu\text{M}\cdot\text{hr}$ in humans, and the highest maternal EBR exposure, AUC_{0-24} = 21.8 $\mu\text{M}\cdot\text{hr}$ (measured in pregnant females in the embryofetal developmental and toxicokinetic [TK] study in rats) represents approximately 16-fold the EBR clinical target AUC_{0-24} of 1.35 $\mu\text{M}\cdot\text{hr}$ in humans. Additionally, EBR and GZR placental and lactational transfer studies in rats and EBR and GZR placental transfer studies in rabbits showed distribution of EBR or GZR into rat and rabbit fetal plasma and rat milk. TK parameters obtained at different animal ages in the repeat-dose EBR and GZR monotherapy studies in rats and dogs did not indicate age-related differences in plasma systemic exposures. In rats, the first TK evaluation was performed in 7-week old animals (which corresponds to an approximate human age of 12 years), and the last TK evaluation was performed in 18-week old animals (adult animals). In dogs, the first TK evaluation was performed in 26- (EBR) or 32-week old (GZR) animals (which corresponds to an approximate human age of 15-17 years), and the last TK evaluation was performed in 56- (EBR) or 78-week old (GZR) animals (adult animals).

In conclusion, pre-clinical animal studies support the use of EBR and GZR in children.

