5.1 Overall Design

This is a non-randomized, single arm, multiple cohort, multi-site, open-label Phase IIb trial of EBR/GZR in pediatric participants aged 3 to less than 18 years with chronic HCV infection GT1b/1-other; GT1a without baseline NS5A RAS at positions 28, 30, 31, and/or 93; or GT4, to be conducted in conformance with Good Clinical Practice.

The goals of this Phase IIb trial are: 1) to define doses for EBR/GZR in children by assessing plasma PK concentrations that target a similar PK to that seen in adults receiving EBR 50 mg and GZR 100 mg. The PK target has been defined by the clinical PK comparability bounds, within which there were no clinically important differences for safety and efficacy; 2) to establish the tolerability, safety, and efficacy of the combination therapy in the pediatric HCV-infected population. All participants will receive EBR/GZR without RBV for 12 weeks.

The trial will enroll participants into three Age Cohorts:

1. Age Cohort 1 (aged 12 years to less than 18 years)
2. Age Cohort 2 (aged 7 years to less than 12 years)
3. Age Cohort 3 (aged 3 years to less than 7 years)

Each Age Cohort starts with a Mini Age Cohort of 7 participants before enrolling additional participants into the Expanded Age Cohort. The enrollment requirements for the Mini and Expanded Age Cohorts are shown in [Table 2](#).

Table 2 Enrollment Requirements for Each Age Cohort

Age Cohort	Age Range	Enrollment Requirements	
		Mini Cohort	Expanded Cohort
1	12 to <18 years	
 • N=7 (to ensure at least 6 participants with evaluable PK) • At least 2 participants aged <14 years 	
 • N=~15 • At least 3 participants aged 12 to <14 years • At least 3 participants aged 16 to <18 years
2	7 to <12 years	
 • N=7 (to ensure at least 6 participants with evaluable PK) • At least 2 participants aged <9 years 	
 • N=~20 • At least 5 participants aged 7 to <12 years • At least 5 participants aged 3 to <7 years 
 ○ At least 2 participants aged <5 years
3	3 to <7 years	
 • N=7 (to ensure at least 6 participants with evaluable PK) • At least 2 participants aged <5 years 	

The enrollment of participants will occur as follows:

1. Mini cohorts of the two oldest Age Cohorts will enroll in the first wave of participants.
 - a. Mini Age Cohort 1
 - b. Mini Age Cohort 2

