7.2 Dose Modification (Escalation/Titration/Other)

Dose modification of EBR/GZR is not permitted by the site personnel. For more information on dose modification during the course of the trial, see Section 5.5.1.1.

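### Section 5.5.1.1: at printed precision, the GZR limits of ~0.81-8.6 µM*hr and the clinical bounds [0.4, 5.0] do not share one adult reference AUC

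*Combined protocol and SAP*

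**What the plan says.** Section 5.5.1.1 (Dose Justifications) sets the exposure criterion for each pediatric age group in three steps.

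- A similarity aim: "The pediatric GM AUC should be approximately within 2-fold that estimated in adults for EBR and GZR".
- The clinical bounds: "the pediatric GM AUC range should fall within the defined clinical bounds for EBR [0.5, 2.0] and GZR [0.4, 5.0". Sections 3.2.3 and 3.2.3.2 give the same bounds and attribute them to the adult PK/PD models for safety and efficacy.
- The bounds in absolute units, introduced as a consequence of the above. The GZR requirement, in µM*hr, is that "the pediatric GM AUC for each age group should fall within ~0.81-8.6". The parallel EBR range runs from about 1.1 to 4.4 in the same unit. The link from these limits back to the bounds is explicit: "which corresponds to the AUC associated with the lower and upper clinical bounds".

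The consequence of falling outside follows directly: "Otherwise, the dose will be adjusted for the Expanded Age Cohorts so that the AUC falls within the clinical bounds". Section 5.1 gives the bounds the same role ("The PK target has been defined by the clinical PK comparability bounds"), and section 7.2 sends readers to this section: "For more information on dose modification during the course of the trial, see Section 5.5.1.1".

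Section 5.5.1.1 names the reference population, adults receiving EBR 50 mg and GZR 100 mg. It gives no adult reference AUC value from which the absolute limits could be reproduced.

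**The concern.** The bounds read as multiples of adult exposure. Section 3.2.3.2 judges a roughly 20% rise in AUC against them. Read as µM*hr, [0.4, 5.0] and [0.5, 2.0] would also conflict with both printed ranges. If each absolute limit is a bound times one adult AUC, the upper-to-lower ratio must be the same on both scales, whatever that AUC is. EBR passes this test and GZR does not.

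At stake is whether an analyst can reproduce a decision threshold. These limits determine when the dose is adjusted for the Expanded Age Cohorts, and the affected drug is the one whose exposure the protocol links to ALT/AST elevation (3.2.3.2, 3.3). If the observed GZR geometric mean fell between the two versions of a limit, one reader would find the criterion met and another would not, both citing 5.5.1.1.

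**Working it through.** **Inputs, all from 5.5.1.1.** GZR bounds 0.4 and 5.0; GZR limits 0.81 and 8.6 µM*hr; EBR bounds 0.5 and 2.0; EBR limits 1.1 and 4.4 µM*hr.

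**Relation tested.** Limit = bound × adult reference AUC, so implied reference = limit / bound. It should be equal at both ends.

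**1. EBR, as a control.**
- Lower end: 1.1 / 0.5 = 2.2 µM*hr.
- Upper end: 4.4 / 2.0 = 2.2 µM*hr.
- Ratios: 4.4 / 1.1 = 4.0 and 2.0 / 0.5 = 4.0.

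The printed EBR range is reproduced exactly with one reference.

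**2. GZR.**
- Lower end: 0.81 / 0.4 = 2.025 µM*hr.
- Upper end: 8.6 / 5.0 = 1.72 µM*hr.
- Ratios: 8.6 / 0.81 = 10.6, against 5.0 / 0.4 = 12.5.
- Gap: 2.025 / 1.72 = 1.18, or 18%.

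The printed GZR range is not reproduced.

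**3. Rounding at printed precision.** Take 0.81 as 0.805-0.815, 8.6 as 8.55-8.65, 0.4 as 0.35-0.45 and 5.0 as 4.95-5.05.
- Limit ratio: 8.55 / 0.815 = 10.5 to 8.65 / 0.805 = 10.7.
- Bound ratio: 4.95 / 0.45 = 11.0 to 5.05 / 0.35 = 14.4.

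The two intervals do not overlap, so rounding at this precision does not close the gap.

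**4. Coarser rounding of 5.0.** Suppose 5.0 stands for a whole-number bound that could be as low as 4.5, and 0.4 for a value up to 0.45.
- The lower end then allows a reference down to 0.81 / 0.45 = 1.80.
- The upper end allows one up to 8.6 / 4.5 = 1.91.

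A reference of 1.80-1.91 µM*hr would fit both ends. For example, at 1.85 the limits are 0.81 / 1.85 = 0.44 and 8.6 / 1.85 = 4.65 times the reference.

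**5. Size of the disputed zones, taking each implied reference with [0.4, 5.0] as printed.**

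| Reference (µM*hr) | 0.4 × reference | 5.0 × reference | 2-fold range |
|---|---|---|---|
| 1.72 | 0.69 | 8.6 | 0.86-3.44 |
| 2.025 | 0.81 | 10.1 | 1.01-4.05 |

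The classification can differ for a geometric mean of about 0.69-0.81 or 8.6-10.1 µM*hr. Both zones lie outside both 2-fold ranges. The printed range, 0.81-8.6, is the overlap of the two candidate ranges.

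**The case against.** The strongest reply is that the documents nowhere state a single reference. The bounds come from adult PK/PD models for safety and for efficacy, so the two ends could rest on different analyses. EBR is also an imperfect control. Section 3.2.3.1 describes EBR PK as linear, with comparable exposure in patients and healthy participants, but GZR PK as non-linear, with exposure about 2-fold higher in patients. The choice of reference therefore matters more for GZR. Step 4 shows that coarser rounding could reconcile the figures as well. All this stands as possibility. None of it is stated, and the sentence presents the EBR and GZR limits in the same way.

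A second reply is that the disputed zones carry little decision value. This largely stands. A geometric mean there already misses the ~2-fold aim, although that aim is approximate and has no stated consequence. Sections 5.5.1.3 and 10.6.2 also select doses by modelling for adult-like exposure, not merely to stay inside the outer limits. And 18% is small beside the sampling error in Table 12, where the GZR interval lies within 44% of the observed mean even with 22 participants.

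Three stronger readings are tempting but unsupported.

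- A reader might infer that 0.81 or 8.6 is a misprint. The documents do not show which figure, if any, is wrong, and the true reference need be neither 1.72 nor 2.03.
- A reader might infer that the printed limits would miss a needed adjustment. For any reference from 1.72 to 2.03 the printed range lies inside the multiples, so it could prompt an extra adjustment but not miss one. Outside that span the documents do not allow a conclusion, because the reference value is not given.
- A reader might take the human AUC in section 3.2.4 ("represents approximately 31-fold the GZR clinical target" AUC of 5 µM*hr) as the reference. It serves animal exposure margins and is not tied to these bounds, so a mismatch with it says nothing about 5.5.1.1.

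**Conclusion.** The point holds as a minor inconsistency. At printed precision, the GZR multiples and the GZR µM*hr limits in 5.5.1.1 do not share one reference: the implied values are 2.03 and 1.72 µM*hr, 18% apart. The EBR figures do share one. The conclusion assumes that the bounds multiply an adult AUC, and that both GZR ends are meant to use the same one. The first is the only reading that fits the text; the second is inferred from EBR. The figures are also marked as approximate. The consequence is confined to a GZR geometric mean close to a limit, so the practical effect is small. It deserves correction because these are the limits on which a dose adjustment turns, and they cannot be reproduced from the protocol. Which limit is right is for the sponsor to determine.

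**What to change.** The sponsor should check the GZR limits against the adult PK data it already holds. Section 5.5.1.1 should then state the adult reference AUC value or values used. Sections 3.2.3, 3.2.3.2 and 5.5.1.1 should be reconciled so that the GZR multiples and the µM*hr limits agree. If the two ends deliberately use different references, 5.5.1.1 should say so. The cost is one data check and a few words of protocol text, with no change to participants, procedures or sample size.

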3.2.3 PK Background and Strategy

In the Phase II/III EBR/GZR development program, population PK, PK/pharmacodynamics (PD), and physiologically based pharmacokinetic (PBPK) modeling supported the proper dosing for a safe and efficacious adult regimen. The PK/PD modeling for safety and efficacy were used to define the clinical comparability bounds, based on an area under the time-concentration curve (AUC) of [0.4, 5.0] for GZR and [0.5, 2.0] for EBR. Application of these models and clinical bounds will be applied to this pediatric trial to support dosing of children aged 3 years up to 18 years.

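### Section 5.5.1.1: no single adult reference AUC gives both limits of the printed GZR dose-adjustment window (~0.81-8.6 µM·hr)

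*Combined protocol and SAP*

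**What the plan says.** Section 5.5.1.1 judges similarity to adults on the GM AUC. It first gives a general aim: "The pediatric GM AUC should be approximately within 2-fold that estimated in adults for EBR and GZR". It then requires the GM AUC to lie inside the clinical bounds, [0.5, 2.0] for EBR and [0.4, 5.0] for GZR. Finally it converts the bounds to absolute units, in µM·hr. The GZR criterion is that "the pediatric GM AUC for each age group should fall within ~0.81-8.6". The EBR counterpart runs from about 1.1 to 4.4. Both windows are presented as the bounds themselves in absolute terms, in the words "which corresponds to the AUC associated with the lower and upper clinical bounds". When the criterion is not met, the stated consequence is this: "Otherwise, the dose will be adjusted for the Expanded Age Cohorts so that the AUC falls within the clinical bounds".

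Other sections give the bounds the same weight. Section 3.2.3 says "Application of these models and clinical bounds will be applied to this pediatric trial", and Section 5.1 says "The PK target has been defined by the clinical PK comparability bounds". Section 7.2 sends readers to 5.5.1.1 for dose modification. Section 10.6.2 says only that a separate modeling and simulation plan may be written.

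Section 5.5.1.1 prints no adult reference GM AUC for either drug. The only human AUC values printed elsewhere are in Section 3.2.4, on animal exposure margins. There the highest maternal rat GZR exposure "represents approximately 31-fold the GZR clinical target" AUC of 5 µM·hr, and the EBR counterpart is 1.35 µM·hr.

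**The concern.** If a window is a pair of multiples applied to one adult value, dividing each limit by its multiple must return that value twice. For GZR it returns two different values. The section therefore holds two versions of the same criterion, one in multiples and one in µM·hr, and they disagree.

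This is the section's only mandatory trigger for changing a dose. A team that works from the multiples and a team that works from the printed limits could decide differently on the same data. GZR is also the drug for which this matters more: Section 3.2.3.2 ties ALT/AST elevations to its exposure, and ties SVR12 to the exposure of both drugs. If no separate modeling plan is written, these printed numbers may be the only prespecified numerical standard.

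**Working it through.** **Inputs.** Bounds: EBR [0.5, 2.0], GZR [0.4, 5.0]. Printed windows: EBR ~1.1-4.4 µM·hr, GZR ~0.81-8.6 µM·hr (all Section 5.5.1.1). Formula: implied adult reference = printed limit / bound.

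**Step 1: EBR, to check the method.** 1.1/0.5 = 2.2 and 4.4/2.0 = 2.2. The window spans 4.4/1.1 = 4.0-fold, and the bounds 2.0/0.5 = 4.0-fold. One reference reproduces the EBR window, which supports reading the bounds as multiples of an adult AUC.

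**Step 2: GZR.** 0.81/0.4 = 2.025 and 8.6/5.0 = 1.72. The window spans 8.6/0.81 = 10.6-fold, and the bounds 5.0/0.4 = 12.5-fold. The implied references differ by 2.025/1.72 = 1.18, about 18%. The plan's GZR window cannot be reproduced.

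**Step 3: rounding.**

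| What is treated as rounded | Reference from lower limit | Reference from upper limit |
|---|---|---|
| Limits only (0.805-0.815; 8.55-8.65) | 2.01-2.04 | 1.71-1.73 |
| Limits and bounds (bounds 0.35-0.45; 4.95-5.05) | 1.79-2.33 | 1.69-1.75 |

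Neither pair overlaps. In the more generous case the printed span is at most 8.65/0.805 = 10.75, and the bounds span at least 4.95/0.45 = 11.0.

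**Step 4: the Section 3.2.4 values as references.** GZR: 5 × [0.4, 5.0] = 2.0-25. EBR: 1.35 × [0.5, 2.0] = 0.675-2.7. Neither matches its printed window, including the EBR window that is internally consistent. These values may be a different quantity.

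**Step 5: illustration only.** The references below are assumptions. The first two are back-calculated from the limits in question, and the third is arbitrary.

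| Assumed adult GZR GM | 0.4 to 5.0 times it | Printed limits as multiples |
|---|---|---|
| 1.72 | 0.69-8.6 | 0.47 and 5.0 |
| 2.025 | 0.81-10.1 | 0.40 and 4.25 |
| 2.2 | 0.88-11.0 | 0.37 and 3.91 |

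**Step 6: how often it might matter, under the first two assumptions.** Take 6 evaluable participants (Table 2) and a log-scale SD of 0.731 (Section 10.9.1). The standard error of the log GM is 0.731/√6 = 0.298.

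- If the reference is 1.72, the disputed strip is 0.40-0.47 times adult. The observed GM falls there with probability 0.5%, 3% and 19% at true ratios of 1.0, 0.8 and 0.5.
- If it is 2.025, the strip is 4.25-5.0 times adult. The probability is below 0.1% up to a true ratio of 1.5, then 0.5% at 2 and 8% at 3.

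The SD comes from adults with advanced cirrhosis and hepatic insufficiency, whereas the Mini Age Cohorts are noncirrhotic. The figures are for a raw GM, while the planned modeling pools pediatric and adult data.

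**The case against.** The strongest reply is that the two GZR limits may rest on different references. Section 3.2.3.2 says the bounds come from PK/PD models for safety and efficacy, and these could have used different adult populations at the two ends. The models are not in the documents, so this cannot be excluded. It stands as a limit on the finding: the mismatch is shown, but a specific wrong limit is not. It does not rescue the text, because the section says nothing of two references and the EBR limits beside them need only one.

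The approximation signs are a weaker reply. EBR carries the same sign and reconciles exactly, and Step 3 shows that rounding is not enough.

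It is also fair that little may turn on this. Doses are re-selected by modeling before each later cohort (Sections 5.1, 5.5.1.3, 10.6.2). Mini Age Cohort 1 already receives the maximum GZR dose of 100 mg (Section 5.5.2), so a low GM there could not raise the dose. Stopping rules (Section 8.1) and an enrollment pause (Section 5.4.2.3.2) cover hepatic safety. All of this stands and limits the severity.

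**Conclusion.** Wrong as written; minor. At least one GZR limit of the dose-adjustment window does not match the bound it is said to represent. That rests on arithmetic and on one assumption, that the bounds multiply a single adult reference, which the EBR window supports. The mismatch is about 18% between the implied references. The primary PK objective is estimation, so no hypothesis test is affected.

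A reader might infer more in three ways, and the documents do not support them:

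- *That the right window is known, as 0.69-8.6 or 0.81-10.1.* Both come from the disputed limits. Any other reference moves both limits.
- *That the printed limits err only on the cautious side.* This holds only for a reference between 1.72 and 2.025. At 2.2 the lower limit would act at 0.37 times adult, which is less cautious than 0.4.
- *That the GZR upper limit should be capped at 2-fold, or that the 2-fold sentence has no role.* Sections 3.2.3 and 5.1 make the clinical bounds the target, and 5.5.1.1 ties adjustment to them, so the action rule is determinate. The 2-fold sentence is an approximate similarity aim, and Sections 5.5.1.3 and 10.6.2 already make similar exposure the goal of each modeling step.

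**What to change.** Take the adult reference GM AUC for GZR from the adult model, not from the printed limits. Print it in Section 5.5.1.1 with the EBR reference, and recompute both GZR limits as 0.4 and 5.0 times that value. If the two limits deliberately use different references, state both and correct the sentence that describes the window. Keep the GZR clinical bounds as they are.

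The cost is a check against an existing model and a wording change in one section, with no new data or participants. The downside is that a printed limit may become slightly wider, so the sponsor should confirm the reference before changing either number.
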